 - a. Justification: MRI is the primary data gathering tool
 - b. Screening tools: current clinical procedures in use at the NIDA IRP

iii. Exclusion Criteria

1. History of any neurological disorder that would increase seizure risk from iTBS such as stroke, brain lesions, previous neurosurgery, any history of seizure or fainting episode of unknown cause, or head trauma resulting in loss of consciousness, lasting over 30 minutes or with sequela lasting longer than one month.
 - a. Justification: Stroke, vascular lesions or head trauma can lower the seizure threshold and are therefore contra-indications for iTBS. Fainting episodes or syncope of unknown cause could indicate an undiagnosed condition associated with seizures.
 - b. Screening tool: TMS safety Screen and Medical History.
2. Current DSM-5 moderate-severe substance use disorder on a substance other than cocaine, nicotine, marijuana, or opiates (provided they are currently stable on a medication assisted treatment) or meeting withdrawal criteria for a sedative/hypnotic/anxiolytic, or tolerance criteria in an individual using 3 or more days/week, regardless of diagnosis. Individuals will be considered stable on a maintenance medication if they have been on a stable dose for at least 2-weeks prior to consenting to 17-DA-N002 and have provided at least 3 urine specimens negative for illicit opioids over the same 2-week period (10 business days) with at least one test collected within two business days of the start of the period, one collected within three business days of the end of the period and one collected at least two days from either

of the other two specimens. Urine results may be gathered at NIDA as part of screening or be provided by the buprenorphine maintenance prescriber.

Communication between the maintenance provider and the MAI (or covering Staff Clinician) will be ongoing to establish continued illicit opioid abstinence between participant clearance and consent to 17-DA-N002.

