- a. Justification: While use of multiple substances is the norm and some use will be allowed, the focus of the current protocol is on cocaine. However, participants with tolerance or withdrawal symptoms to a sedative/hypnotic/ anxiolytic will be at increased risk of a seizure from iTBS and will therefore be excluded. Alcohol withdrawal will be assessed on ITBS days and rescheduled if in withdrawal. Individuals receiving maintenance treatment for OUD and struggling with cocaine use are an ecologically valid population in the greater Baltimore area and do not increase risk of seizure.
- b. Screening tool: Drug Use Survey and SCID-research version.

3. HC participants will not currently meet DSM-5 criteria for moderate to severe substance use disorder (excluding nicotine), and in the past, will not meet DSM-5 criteria for moderate to severe substance use disorder for cannabis or alcohol in the past 5 years or ever for other illicit substances. HC will not meet current withdrawal criteria for alcohol or sedative/hypnotics/anxiolytics, or tolerance criteria in an individual using 3 or more days/week. Urine toxicology positive for any illicit substance inconsistent with history given will also be exclusionary.

- a. Justification: The population of interest is a healthy control population with no substance use disorder. Current use of illicit substances or alcohol could impact on seizure threshold and is therefore contraindicated for iTBS.
- b. Screening tools: SCID-research version. Potential diagnoses will be further evaluated by a counsellor, Drug Use Survey (DUS), Substance

Use Disorder Evaluation, Medical Assessments: urine qualitative drug screen is performed for cocaine, THC, benzo, morphine/opiates, MDMA, amphetamine /methamphetamine, methadone, buprenorphine, PCP, and oxycodone.

4. First-degree family history of any form of epilepsy with a potentially hereditary basis .
 - a. Justification: First-degree family history of epilepsy with a hereditary component increases the risk of the participant having an undiagnosed condition that is associated with lowered seizure threshold.
 - b. Screening tool: TMS safety screening, Medical History.

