Protocol completers are defined as CD participants who complete 10 iTBS days of treatment within 3 weeks and visit 19 (first post-treatment scan day). CD participants who complete at least 5 iTBS treatment days in 3 weeks are eligible to begin with CM and follow-up visits. All study visits, including those with MRI scans, will be offered to these individuals as if they had completed all 10 iTBS treatment days. An HC participant is considered a protocol completer after completing all scheduled visits (baseline characterization visits and 2 iTBS treatment days with MRI scans).

Overall, CD participants will complete about 43 visits and HC participants 5 visits, with 8 and 6 MRI scans collected for CD and HC participants, respectively. Most of the visits for CD participants will be to collect urine samples and implement CM. The order of procedures completed during each visit may vary slightly, depending on availability of staff and other resources (mock scanner, MRI, study rooms, etc.).

Each study visit day will start with a brief nursing assessment that includes a urine sample for drugs of abuse, a breathalyzer, and vital signs. A urine pregnancy test for females will occur weekly during the iTBS treatment and any visit that includes an MRI scan thereafter. If breathalyzer is positive for alcohol participants may be rescheduled. In the event of a positive drug test, an interview to assess last drug use and a neuromotor assessment to test for acute intoxication will be performed. If participants test positive for drugs other than marijuana, based on MAI judgment, they may be rescheduled. If urine is positive for other illicit drugs, and if there are no known TMS contraindications, the participants may be allowed to participate at the discretion of the MAI. Otherwise, participants will be rescheduled. The CD group is expected to be current users and will likely test positive for illicit drugs. These procedures are designed to identify if CD participants are currently impaired and if HC participants have recently used illicit or licit drugs. Participants who smoke will be allowed breaks to smoke to preclude acute nicotine withdrawal. If a participant runs out of cigarettes, we will provide them on an as-needed basis to avoid withdrawal, which requires us to reschedule the visit. All study visits will take place at National Institute on Drug Abuse Intramural Research Program (NIDA-IRP).

1. Screening

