(https://oma.od.nih.gov/DMS/Documents/Records/NIH_Intramural_Research_Records_Schedule.pdf) for 7 years after the completion of the study or when no longer needed for scientific reference, whichever is longer. This footage may be used by the MAI and any experts the MAI wishes to consult to determine the nature of the event. Participants will not be given the option to opt out of the video recordings. If they do not wish to be recorded, the alternative is to not participate in the study.

MRI: At screening and on each study day involving an MRI scan, participants will fill out an MRI safety form to ensure that there is no change in the participant's suitability for MRI scanning. They will also have a urine drug screen and pregnancy test (females).

If urine drug screen is positive for drugs other than cocaine and THC, they will be rescheduled; if pregnant, females will be notified, referred if necessary for care, and discontinued from participation in the study. At all times during MRI scanning study, a scan operator will be present in the control room and participants will be able to communicate via an intercom. Participants will also have a device they can squeeze to alert the operator in case of an urgent issue.

Acute clinical needs: 'Red flags' observed during clinical assessments will be used to identify acute clinical needs. The first-level evaluation is participant interaction with a nurse at intake. NIDA nurses are well trained to identify abnormal behavior that may need immediate clinical attention. When such behavior is identified, a flag will be generated and the MAI will be contacted. A second flag level is programmed into the CDW system to be triggered if a participant endorses a specific state. The LAI will routinely review CDW files for such flags while the participant is at NIDA-IRP. A failsafe mechanism is in place such that remuneration cannot be disbursed with an unaddressed red flag. Therefore, participants who endorse specific states during a visit will be identified and assessed by clinical staff prior to discharge for the day.

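### The MRI-day urine rule makes rescheduling mandatory without exempting the prescribed opioid maintenance medication that eligibility allows, and it conflicts with the discretionary rules for the same visits

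*Combined protocol and SAP*

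**What the plan says.** The MRI paragraph of section IV.C sets its own occasions: "At screening and on each study day involving an MRI scan, participants will fill out an MRI safety form". A urine drug screen is taken on the same occasions. The consequence of a positive follows: "If urine drug screen is positive for drugs other than cocaine and THC, they will be rescheduled". The paragraph states no exception for prescribed medication and gives the MAI no discretion.

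Eligibility points the other way. Exclusion criterion 2 (section III.F.iii) bars most other moderate-to-severe substance use disorders but makes an exception for nicotine, marijuana "or opiates (provided they are currently stable on a medication assisted treatment". Stability is judged partly by "at least 3 urine specimens negative for illicit opioids over the same 2-week period", so the criterion separates illicit from prescribed opioids. The justification says these people are wanted: "Individuals receiving maintenance treatment for OUD and struggling with cocaine use are an ecologically valid population in the greater Baltimore area". It adds that they bring no added seizure risk.

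Two other rules govern positive urines in the same phase of the study. Section III.G.i (Study Procedures) says: "If participants test positive for drugs other than marijuana, based on MAI judgment, they may be rescheduled". It then lets the MAI allow participation after other illicit positives when nothing contraindicates TMS, and continues: "Otherwise, participants will be rescheduled. The CD group is expected to be current users and will likely test positive for illicit drugs". Section III.G.i.2 (Nursing Assessments) also leaves rescheduling to the MAI. It exempts THC for everyone and cocaine for the CD group only, and it allows exclusion after a second positive. Section III.G.i.3 requires that nursing assessment at every scan session.

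**The concern.** Rescheduling suits recent illicit use, because the participant can return with a clear urine. It does not suit a drug taken daily under a stable prescription, which would be expected to show again at the next attempt. Followed as written, the IV.C rule would keep deferring a person whom the eligibility criteria admit on purpose.

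The scans matter because section IV.C.ii names fMRI change as the primary outcome of interest. Visits 1 and 2 are scan days, and visit 3 is both a scan day and the first iTBS day (section III.E). A participant held at the first scan would therefore reach neither baseline imaging nor treatment.

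Staff also have two instructions for one urine on one day: a mandatory rule in IV.C and a discretionary rule in III.G.i and III.G.i.2. The protocol does not say which prevails.

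**Working it through.** The plan gives no figure for this point, so the check sets the rules side by side.

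| | IV.C, MRI paragraph | III.G.i, Study Procedures | III.G.i.2, Nursing Assessments |
|---|---|---|---|
| Applies | Screening and each MRI day | Each study visit day | Before study sessions; extended to each scan session by III.G.i.3 |
| Positives exempted | Cocaine and THC, any group | Marijuana | THC; cocaine for CD only |
| Consequence of another positive | Mandatory rescheduling | Possible rescheduling; mandatory as the fallback after the sentence on illicit drugs | Possible rescheduling; possible exclusion on a second positive |
| MAI discretion | None stated | Yes | Yes |
| Mentions prescribed maintenance medication | No | No | No |

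None of the three rules (0 of 3) says what to do with a positive explained by maintenance treatment. III.G.i.2 does have staff ask about recent prescription intake, so they would be able to recognise one.

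**Would the urine show the drug?**

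1. At screening, yes by design. The qualitative panel under Medical Assessments in III.G.i.1 lists methadone and buprenorphine. I assume that a panel listing a drug detects it when it is taken as prescribed.
2. On scan days, this is not stated. The urine-test paragraph in III.G.i.2 speaks of many prescribed and non-prescribed drugs, but it also describes the dip card as a screen for cocaine metabolite. No scan-day list of drugs is given.

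**What the literal IV.C rule then does to a participant taking methadone or buprenorphine as prescribed**

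1. At screening, the panel lists the drug, so the result is positive and the participant is rescheduled. The repeat would be expected to be positive too.
2. At visit 1, the first scan day, the same happens if the scan-day panel matches the screening panel. If that panel does not include the drug, the rule is not triggered.
3. At later scan days, a participant held at an earlier step does not arrive.

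The size for one participant is therefore a single obstacle, met at the first occasion on which the screen covers the drug. Under III.G.i and III.G.i.2 alone, the MAI could let the same participant through.

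**How many participants?** With 90 CD participants to be enrolled and a share *m* taking methadone or buprenorphine, the number exposed is 90 × *m*. The documents do not give *m*, so no count can be made.

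**The case against.** The strongest reply is that the MAI already has the authority and the information to avoid the problem. III.G.i and III.G.i.2 cover the same visits and make rescheduling a matter of judgment. The nursing assessment records prescription intake. Exclusion criterion 2 puts the MAI in contact with the maintenance provider before consent. The fallback to rescheduling in III.G.i follows a sentence about illicit drugs, and a prescribed drug is not illicit, so the discretionary sentence before it fits better. Much of this stands: an MAI reading the protocol as a whole would probably let the participant proceed. Doing so still departs from the mandatory wording of IV.C, and no text says that departure is allowed.

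A second reply is that the scan-day panel may not include the maintenance drugs. That also stands, and it is why the effect on scan days can only be conditional. It does not remove the conflict at screening, where IV.C also applies and the panel is listed.

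Three stronger readings are tempting, and the documents do not support them.

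- **Every scan is lost.** CD participants have 8 scans over 5 scan days, and a reader might infer that all 5 days would be deferred. A participant blocked at visit 1 never reaches the other four, so that count repeats one obstacle.
- **The control comparison is contaminated.** IV.C exempts cocaine without naming a group, so a reader might infer that a cocaine-positive healthy control (HC) would be scanned as a non-user. IV.C lists what forces rescheduling; it does not order anyone to be scanned. III.G.i.2, which applies at every scan session, exempts cocaine only for CD participants. Exclusion criterion 3 bars controls whose urine shows an illicit substance at odds with their stated history. Section IX.G withdraws controls who need rescheduling more than twice for positive urine.
- **The treatment comparison or its power suffers.** Nothing suggests that the rule acts differently on active and sham iTBS, and it changes none of the inputs to the sample-size calculation.

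**Conclusion.** The point holds as an inconsistency between rules. IV.C requires rescheduling for a positive that eligibility anticipates and that rescheduling cannot clear, while III.G.i and III.G.i.2 leave the same positive to the MAI. The conflict is plain from the text at screening. On scan days it depends on the assumption that the panel there also covers methadone or buprenorphine. In practice MAI discretion probably prevents the deferral. The number of participants affected is unknown. Severity is minor, and this is a correction to procedural wording, with no change needed to the statistical design.

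**What to change.** In the MRI paragraph of IV.C, keep mandatory rescheduling but list three exemptions: THC; cocaine, for CD participants only; and a verified, prescribed maintenance medication for opioid use disorder. Limiting cocaine to CD participants simply brings IV.C into line with III.G.i.2.

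In III.G.i and III.G.i.2, add that a positive explained by verified, prescribed maintenance medication is not a reason to reschedule and does not count toward exclusion on a second positive.

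The change needs no additional urine test, scan or visit. It does have a cost: the prescription may need re-confirming after consent. Exclusion criterion 2 describes contact with the maintenance provider only up to consent, while scans continue to week 14. The release allowing contact during enrolment is described in the Pilot section (II.E.i.3), so the Expanded Feasibility Study should provide for an equivalent.

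This wording does not settle whether the mandatory or the discretionary rule governs other positives on MRI days. One sentence giving IV.C precedence on those days would do so.
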